**I. BACKGROUND AND SIGNIFICANCE**

**a. Historical background**

Major depressive disorder (MDD) occurs twice as often in women as in men, with an age of onset that coincides with the childbearing years. As over 20% of reproductive-age women experience an episode of depression, identifying safe and effective treatments for depression before, during and after pregnancy has become a critical public health issue.

Historically, pregnancy has been viewed as a protective time with respect to risk for psychiatric illnesses such as MDD. This assumption has resulted in a lack of prospective systematic investigations on the subject of acute treatment and prevention of MDD while women are planning to conceive and during pregnancy. Contrary to previous assumptions, recent large-scale studies demonstrate that new onset and recurrence of depressive episodes occur commonly during pregnancy and the postpartum period. The current standard of treatment for recurrent MDD is maintenance antidepressant (AD) therapy(1). These guidelines are derived from the high risk of recurrence among patients who discontinue maintenance AD therapy. Although ADs are frequently used during pregnancy, concerns remain regarding a spectrum of adverse outcomes associated with fetal exposure to these medications including: increased risk for teratogenicity, compromised obstetrical outcomes, and a variety of negative neonatal clinical syndromes(2). Given these concerns, reproductive age women treated with ADs frequently elect to discontinue their medications proximate to pregnancy or immediately after becoming pregnant despite the known increased risk for relapse or recurrence. Women who experience depressive episodes during pregnancy or while trying to conceive often forgo antidepressant use. With the exception of observational data that demonstrate that women who discontinue medication around the time of conception are at high risk of recurrence, no previous studies are available to inform clinical treatment regarding medication discontinuation for a planned pregnancy(3).

This leaves women in the difficult clinical dilemma of weighing the risks of fetal exposure to medication against the potential impact of untreated maternal depression during pregnancy. Clinical decisions are made even more complex by the fact that most studies are far from definitive in terms of comparing the risks of in utero exposure to ADs to the risks of untreated antenatal mood disorder. Given this level of uncertainty, many women and their health care providers would welcome evidence-based non-psychotropic interventions as an alternative to ADs in order to treat or prevent depressive episodes in women who are pregnant or planning pregnancy.

However, the potential efficacy of non-psychotropic interventions for the purposes of acute treatment and recurrence prevention following AD discontinuation among women who plan to conceive or for those who are pregnant has received limited study.

**b. Previous pre-clinical or clinical studies leading up to and supporting the research**

## Partners Human Research Committee Detailed Protocol

In the following sections we review literature in several critical areas pertaining to the proposed investigation: evidence confirming that depression is often a recurrent illness; knowledge of the prevalence and outcomes of depression and its treatment across pregnancy; studies examining the reproductive safety of AD use during pregnancy, data suggesting that women often discontinue maintenance AD use proximate to conception despite an increased risk for relapse and recurrence; and investigations specific to the use of methylfolate in the treatment of MDD and for improved pregnancy outcomes.

### Depression is a Recurrent Illness

A growing body of literature indicates that MDD is most often a recurrent illness. The clinical term used to describe a depressive episode that reappears within six months of acute response is a relapse while symptoms that occur after six months of euthymia are called recurrences(4). Relapses are considered a return of the original episode, whereas recurrences represent a new episode. Although these distinctions are based on limited data, the phases of treatment to prevent relapse and recurrence have been differentiated correspondingly into continuation and maintenance phases, respectively.

Observational Studies. Data derived from the National Institute of Mental Health Collaborative Program on the Psychobiology of Depression (n=380) were examined to investigate the proportion of patients experiencing a recurrence of MDD up to 15 years after recovery from the index episode(5). The vast majority of patients (85%) experienced a recurrence during this time period, with those remaining well 5 years after recovery experiencing a rate of recurrence of 58%. Results from the Collaborative Program study (n=359) revealed a 20% relapse rate and an overall 88% recurrence rate (within five years of recovery)(6). These findings are even more compelling as these patients had received “high levels of somatic treatment” during the entire observation period. Other observational studies have confirmed high rates of relapse and recurrence in patients with and without optimal psychopharmacologic management(7-9).

Randomized Controlled Trials. Data from randomized controlled trials, typically using a double-blind discontinuation method, reveal that long-term treatment with ADs lowers the risk for relapse and recurrence when compared with placebo substitution (9-11). However, even while taking ADs for prophylaxis, up to 20-80% of patients develop another depressive episode within five years after treatment for the initial episode (6, 12-14). One recent meta-analysis pooled data from 31 randomized trials and found that maintenance AD therapy (following acute treatment) reduced the odds of relapse and recurrence by 70% compared with treatment discontinuation(15). The average rate of relapse on placebo was 41% compared with 18% on active treatment. The proportional risk reduction was found to be similar in patients with short (6 months) and long (36 months) follow-up periods, which suggests that time since response does not affect risk.

Guidelines for preventing recurrence. The observational studies and randomized controlled trials above have informed the development of recognized clinical treatment guidelines, which support the use of long term AD treatment to prevent relapse and recurrence, especially for patients described as at high risk due to clinical factors(1, 16, 17). These risk factors include a history of three or more depressive episodes, two or more depressive episodes within five years, a family history of bipolar disorder or recurrent depression, early-onset depression, and previous recurrence within one year of medication discontinuation. Additionally, individual risk factors including patient preference, suicide risk, episode severity, social support, and life stressors, influence every treatment response.

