Prevalence of AD Use during Pregnancy. As previously demonstrated, based on data derived from health insurance and hospital records, investigators found that ADs were prescribed to nearly 8% of all pregnant women(2). The investigators found that AD use during pregnancy increased from 2.0% of all deliveries in 1996 to 7.6% of all deliveries in 2004 and 2005, with consistently more women dispensed an AD during the first trimester of pregnancy than in either the second or the third trimester. Clinicians must weigh the morbidity associated with depressive relapse and recurrence in the mother against the risk of adverse birth outcomes that may be associated with medication exposure for the fetus. In order to avoid fetal exposure to ADs where attendant risks of in utero exposure is incompletely delineated, many women discontinue these medicines regardless of risk for recurrence.

High Risk of Relapse of Depression during Pregnancy among Women who Discontinue Maintenance AD Therapy. Studies conducted over the last decade have demonstrated that prevalence of depression during pregnancy is similar to age-matched non-pregnant women, replacing previously held ideas that pregnancy was protective against psychiatric illness. Left untreated, depression can negatively impact both the mother and the fetus. For women with histories of MDD who discontinue AD medication to avoid fetal drug exposure, the risk of depressive relapse is high. In a multi-site NIMH funded collaborative study, the rate of depressive relapse among women with a history of MDD who discontinued ADs (68%) was significantly higher than the rate (26%) for women who maintained AD treatment(3). In this study, continued AD treatment during pregnancy significantly reduced the risk of maternal depressive relapse. Data from this large scale, multi-site study also demonstrated that there is a broad distribution of AD use early in pregnancy that is not wholly determined by severity of illness as defined by number of episodes of MDD. In fact, there was no association between the decision to discontinue medication during pregnancy and duration of illness, number of previous episodes, or frequency of co-morbid psychiatric illness.

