### **Treatment Decisions during Pregnancy Are Not Driven by Illness Severity**

In a naturalistic prospective study, investigators found that over 43% of women discontinuing AD medications due to pregnancy concerns relapsed, over 50% during the first trimester(3). It could be expected that without random assignment to participation in the study, the participants who elected to enroll would be those with the least severe depression histories. This presumes patients with a history of multiple episodes would disproportionately choose to continue pharmacologic treatment, as compared to women with histories of fewer or more mild illness. However, data from a large scale, multi-site study conducted Cohen, et al. show that there is a broad distribution of AD use early in pregnancy in patients that is not wholly confounded with severity of illness as defined by number of episodes of major depression. We found no association between the decision to discontinue medication during pregnancy and duration of illness, number of previous episodes, or frequency of co-morbid psychiatric illness(3).

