## Partners Human Research Committee Detailed Protocol

have decided to stop ADs (Group 1). Relapse rates for women in this context have been demonstrated to be high, with 68% relapse rates in a large multisite NIMH-funded trial.

**Specific Aim 1b:** To evaluate the efficacy of EnBrace when used as an acute treatment for MDD in a group of women (N=10) who are trying to conceive or are early in pregnancy (Group 2). Women will have major depressive episodes in this group, and may receive EnBrace as monotherapy, or as an adjunct to current pharmacotherapy.

*Hypothesis 1a:* We hypothesize that relapse rates will be lower for women who receive EnBrace compared to historical controls. MDD relapse will be determined by the Mini-International Neuropsychiatric Interview (MINI) mood module that will be administered by a study clinician at each visit.

*Hypothesis 1b:* We hypothesize that the majority of women who receive EnBrace will experience a response (50% improvement in depressive symptoms) to EnBrace therapy.

**Specific Aim 2:** To identify biological markers as potential predictors of response to EnBrace.

*Hypothesis 2:* We hypothesize that pre- to post-treatment changes in homocysteine, folate, B12, IL-6 and CRP will be associated with response to EnBrace. We hypothesize specifically that levels of folate and B12 will increase and homocysteine will decrease temporally with treatment and be predictive of prevention of depressive episodes. We hypothesize that treatment will lower IL-6 and CRP levels due to the anti-inflammatory components of EnBrace (i.e., omega-3 fatty acids) and that decreased levels of inflammatory markers may predict lower risk of depressive relapse in participants who enter the study while not on a depressive episode (Group 1), and will predict response to treatment in women who enter the study while in a depressive episode (Group 2).

**Specific Aim 3 (Exploratory):** To identify factors influencing adherence to and tolerability of treatment. This will be achieved by using qualitative methods to explore (a) perceived risks and benefits of treatment; (b) perceived side effect profile; (c) treatment convenience; (d) knowledge of, attitudes towards, and preferences for depression treatment while attempting to conceive or early pregnancy.

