## V. BIOSTATISTICAL ANALYSIS

We will compare the rates of depressive relapse and duration of time out of a depressive episode for Group 1 participants, and compare these data to historical controls that were also assessed prospectively. For Group 2, we will compare depressive response rates (response defined as 50% reduction in depressive symptoms on the MADRS, our primary outcome) to response rates in studies of SSRIs for the treatment of depression.

In addition, we will monitor depressive symptom burden with continuous variables across the treatment study for both groups.

To control for prenatal vitamin (PNV) use, we will supply a standard PNV to each participant to take daily in combination with EnBrace. The Sponsor has offered to supply the PNV, such that each participant will take the same PNV; this will lower the risk of inconsistencies between participants. In the statistical analysis, the data collected in this preliminary study will be compared to historical controls with a history of MDD who discontinued AD maintenance therapy during pregnancy, most of which were taking standard PNVs, but not EnBrace. This reference will allow us to estimate the relative efficacy of EnBrace in relapse prevention of women who discontinue maintenance ADs for pregnancy.

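### Section V reads the Group 1 comparison with historical discontinuers as EnBrace's relative efficacy, but an uncontrolled 12-week arm of 10 women set against 68% cannot isolate a product effect

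*Combined protocol and SAP*

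**What the plan says.** Hypothesis 1a in Section II reads: "We hypothesize that relapse rates will be lower for women who receive EnBrace compared to historical controls". The figure offered for those controls is in Aim 1a: "Relapse rates for women in this context have been demonstrated to be high, with 68% relapse rates in a large multisite NIMH-funded trial". Section V compares the relapse rate, and the time spent out of an episode, with historical controls who stopped antidepressants during pregnancy. It then states the inference: "This reference will allow us to estimate the relative efficacy of EnBrace in relapse prevention of women who discontinue maintenance ADs for pregnancy".

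Other parts of the protocol bear on that sentence:

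- **Design.** Section III.b plans 10 women for Group 1. The schedule of assessments has seven visits over weeks 0 to 12. No placebo, blinding or concurrent control is described, and a study clinician judges relapse with the MINI mood module at each visit.
- **Controls.** Section V says they too were assessed prospectively and that most took standard prenatal vitamins. It gives neither their visit frequency nor their length of follow-up.
- **Source of the 68%.** Aim 1a calls it a trial. Section I.a calls the evidence under the same citation observational, and the subsection on treatment decisions and illness severity introduces it with "In a naturalistic prospective study". That subsection gives relapse among discontinuers as over 43%, again under the same citation.
- **Other relapse evidence.** For a meta-analysis of 31 randomised trials, the subsection on depression as a recurrent illness reports: "The average rate of relapse on placebo was 41% compared with 18% on active treatment". Section V does not use this figure.

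**The concern.** Relative efficacy is a claim about what the product adds. This design cannot supply it. Women in Group 1 replace an antidepressant with a product they know is being studied for depression, and many will be recruited because they want an alternative (Section III.b). The unblinded study clinician also knows what they take. Their follow-up is fixed at 12 weeks, while the period behind the 68% is not given. Eligibility includes women still planning pregnancy and women whose taper is already complete, whereas Section V describes the controls as stopping during pregnancy.

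Expectancy and shorter follow-up would both tend to lower the observed rate relative to 68%; selection could move it either way. As written, Section V would attribute the net difference to EnBrace. Section II says these data will be used to develop a randomised trial, so a mixed difference labelled as efficacy could carry over into that trial's assumed effect.

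**Working it through.** **Inputs from the protocol.** n = 10 in Group 1; 12 weeks of follow-up; 68% (Aim 1a and Section I.b); over 43% (Section I.b, same citation); 41% on placebo and 18% on active treatment (Section I.b). The protocol gives no test, significance level or power for Group 1.

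**Check of the protocol's own figure.** The crude odds ratio from 18% and 41% is (0.18/0.82) / (0.41/0.59) = 0.316, a 68.4% reduction in odds. This agrees with the stated 70%, since a pooled odds ratio need not equal the crude one.

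**How often would 10 women fall below 68%?** An observed rate below 68% means 6 or fewer relapses. With X ~ Binomial(10, p):

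| True 12-week risk p | Assumption | P(X ≤ 6) |
|---|---|---|
| 0.68 | risk equals the benchmark | 0.40 |
| 0.55 | inert product, modest non-drug effect | 0.73 |
| 0.50 | inert product, larger non-drug effect | 0.83 |
| 0.41 | inert product, risk equal to the cited placebo rate | 0.94 |

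**Follow-up alone.** Suppose 68% accrued at a constant hazard over T weeks. Then the 12-week risk is 1 − (1 − 0.68)^(12/T). Neither the constant hazard nor T is in the documents, so I take T from 24 to 40 weeks.

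- T = 24: 1 − 0.32^0.5 = 0.434, and P(X ≤ 6) = 0.92.
- T = 40: 1 − 0.32^0.3 = 0.290, and P(X ≤ 6) = 0.99.

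These cases assume no product effect and no placebo effect.

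**If a formal test were added.** Under p = 0.68, P(X ≤ 3) = 0.0155 and P(X ≤ 4) = 0.064, so an exact one-sided 5% test (my assumption) would require 3 or fewer relapses. An inert product would pass with probability 0.36 at p = 0.41. It would pass with probability 0.30 to 0.68 under the follow-up illustration (T = 24 to 40). Testing against 68% therefore does not cure the problem.

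**Dependence on the benchmark.** If 43% were the reference, falling below it would need 4 or fewer relapses. At p = 0.41 that has probability 0.61, against 0.94 when the reference is 68%. The choice between two figures carrying the same citation changes the reading materially.

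**The case against.** The strongest reply is that this is a pilot. Section II calls the data preliminary and names a randomised trial as the next step, and lack of control for expectancy is a known limit of any single-arm study. No formal test is planned. The controls were also followed prospectively, so study contact is not shown to be absent from the benchmark. All of this stands. It justifies the design and confines the contact argument to a possible difference in intensity, but it does not justify the efficacy sentence in Section V.

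A reader might go further and treat the difference between 68% and 41%, 27 points or a relative reduction of 1 − 0.41/0.68 = 40%, as the size of the placebo and contact effect. The documents do not support that. The 41% comes from trials not described as pregnancy trials, with follow-up of 6 to 36 months; the 68% comes from women stopping around pregnancy. Against the other figure of over 43%, the gap to 41% is about 2 points. Nor can pregnancy be ruled out as an explanation on the ground that "prevalence of depression during pregnancy is similar to age-matched non-pregnant women": that sentence concerns prevalence, not relapse after stopping treatment, and the subsection on prevalence in pregnancy says pregnancy may be a time of great risk for recurrence.

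It is also tempting to make 41% a success threshold. A two-sided 95% exact interval lies wholly below 41% only at 0 of 10 relapses (upper limit 31%; at 1 of 10 it is 44.5%). With a true risk of 18% that happens with probability 0.82^10 = 0.14. Conversely, under a constant hazard, 41% over 26, 52 or 156 weeks becomes 22%, 11% or 4% at 12 weeks. An inert product would then meet a one-sided rule of 1 or fewer relapses with probability 0.33, 0.68 or 0.94. The threshold would be both too strict and open to false claims.

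**Conclusion.** The concern holds as a limit on inference. A Group 1 relapse rate below 68% cannot be read as EnBrace's relative efficacy, because expectancy, possible differences in contact intensity, shorter follow-up and selection are not separated from the product. Under either illustration, an inert product would very probably give a favourable point estimate: 0.94 at an assumed true risk of 41%, and 0.92 to 0.99 if 68% accrued at a constant hazard over an assumed 24 to 40 weeks. These figures show that the comparison is uninformative about the product. They do not measure any one source of bias, and the documents do not allow the placebo or contact component to be sized. The unexplained 68% and over 43% from one citation leave the benchmark itself unsettled.

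**What to change.** 1. In Section V, replace the relative-efficacy sentence with a statement that the comparison is descriptive and that any difference combines EnBrace with expectancy, study contact, follow-up length and selection.
2. Report the Group 1 relapse proportion with an exact 95% interval and draw no efficacy conclusion from it.
3. Before using either figure as the benchmark, reconcile 68% with the figure of over 43%, and state the population and follow-up to which the chosen figure applies.
4. In Aim 1a, call the source an observational study.
5. If 41% is shown, label it as context from general depression trials with 6 to 36 months of follow-up, and do not use it as a decision threshold.

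These are wording changes plus a check of the cited source. They need no extra women, visits or data. The cost is a less favourable stated conclusion for Aim 1a.

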### Course and Treatment of Depression during Attempts to Conceive and During Pregnancy

## Partners Human Research Committee Detailed Protocol

Prevalence of Depression during Pregnancy. MDD is not only a seriously debilitating illness affecting many people worldwide, but it is particularly critical in the field of women's health. MDD is twice as prevalent in women as in men, with incidence clusters during the reproductive years, as over 20% of women experience an episode of depression during this time(18, 19). Despite a lack of supportive data, pregnancy has historically been considered protective against both the emergence and recurrence of depressive symptoms. Contrary to this belief, both epidemiological data and a recent naturalistic study suggest that, pregnancy may be a time of great risk for recurrence and new onset of depression. The limited epidemiological studies conducted in pregnant adults reveal prevalence rates of moderate and severe depressive symptoms ranging from 6.9% to 20%(18, 20). The risks of untreated depression during pregnancy are significant and include poor nutrition, inadequate weight gain, poor prenatal care, inability to care for oneself, the use of cigarettes, alcohol, or other substances, ambivalence or even termination of the pregnancy, and an increased risk for postpartum depression(21-23). Postpartum depression, a condition only recently understood, is best predicted by the presence of depression during pregnancy, thus it is of critical importance to prevent the emergence of depressive symptoms during pregnancy(24).

Depression during pregnancy is a major public health concern, given its prevalence, and the implicit treatment dilemma of weighing the unknown effects of fetal AD exposure against the effects of untreated depression on 1) maternal well being, 2) obstetrical and neonatal outcomes, and 3) long term development of the child.

Prevalence of AD Use during Pregnancy. As previously demonstrated, based on data derived from health insurance and hospital records, investigators found that ADs were prescribed to nearly 8% of all pregnant women(2). The investigators found that AD use during pregnancy increased from 2.0% of all deliveries in 1996 to 7.6% of all deliveries in 2004 and 2005, with consistently more women dispensed an AD during the first trimester of pregnancy than in either the second or the third trimester. Clinicians must weigh the morbidity associated with depressive relapse and recurrence in the mother against the risk of adverse birth outcomes that may be associated with medication exposure for the fetus. In order to avoid fetal exposure to ADs where attendant risks of in utero exposure is incompletely delineated, many women discontinue these medicines regardless of risk for recurrence.

High Risk of Relapse of Depression during Pregnancy among Women who Discontinue Maintenance AD Therapy. Studies conducted over the last decade have demonstrated that prevalence of depression during pregnancy is similar to age-matched non-pregnant women, replacing previously held ideas that pregnancy was protective against psychiatric illness. Left untreated, depression can negatively impact both the mother and the fetus. For women with histories of MDD who discontinue AD medication to avoid fetal drug exposure, the risk of depressive relapse is high. In a multi-site NIMH funded collaborative study, the rate of depressive relapse among women with a history of MDD who discontinued ADs (68%) was significantly higher than the rate (26%) for women who maintained AD treatment(3). In this study, continued AD treatment during pregnancy significantly reduced the risk of maternal depressive relapse. Data from this large scale, multi-site study also demonstrated that there is a broad distribution of AD use early in pregnancy that is not wholly determined by severity of illness as defined by number of episodes of MDD. In fact, there was no association between the decision to discontinue medication during pregnancy and duration of illness, number of previous episodes, or frequency of co-morbid psychiatric illness.

